7.4 Dosage Modification

For participants in Part 1 and Part 1A who complete DLT observation period (first cycle), and participants in Part 1B and Part 2, study treatment may be modified to manage toxicity. Adverse events should be graded and managed according to NCI CTCAE (version 4.0) guidelines. There are no dose modifications for nivolumab or ipilimumab, except treatment delay. Trametinib dosing will be adjusted as described in [Section 7.4.4](#). If adverse events are considered to be related to study treatment, every attempt must be made to attribute individual study treatment to adverse event, if possible, or to the combination regimen, nivolumab/ipilimumab/trametinib combination or nivolumab/trametinib combination.

- For adverse events that are deemed to be related to trametinib ONLY by the treating physician, dose modification criteria for trametinib must be followed as described in [Section 7.4.4](#) and [Appendix 6](#)
- For adverse events that are deemed to be related to nivolumab or nivolumab in combination with ipilimumab ONLY by the treating physician, dose modification criteria for nivolumab/ipilimumab must be followed as described in [Section 7.4.1](#) and [Appendix 5](#)
- For adverse events that are possibly related to the combination regimen, either nivolumab + trametinib or nivolumab + ipilimumab + trametinib, the most conservative toxicity management guidelines must be followed. Refer to [Section 7.4.3](#) and [Appendix 6](#) for trametinib, and [Section 7.4.1](#) and [Appendix 5](#) for nivolumab + ipilimumab.
- For adverse events that are deemed to be related to regorafenib by the investigator, refer to local product label and institution guidelines for further detail in addition to the recommendation provided in [Section 7.4.6](#).

7.4.1 Nivolumab/Ipilimumab Dose Delay

Nivolumab or ipilimumab administration should be delayed for the following:

- Grade 2 non-skin, drug-related adverse event, with the exception of fatigue
- Grade 2 drug-related creatinine, AST, ALT, and/or Total Bilirubin abnormalities
- Grade 3 skin, drug-related adverse event

- Grade 3 drug-related laboratory abnormality, with the following exceptions:
 - Grade 3 lymphopenia or asymptomatic amylase or lipase does not require dose delay
 - Grade ≥ 3 AST, ALT, Total Bilirubin will require dose discontinuation (see [Section 8.1.1](#))
- Any adverse event, laboratory abnormality, or intercurrent illness which, in the judgment of the investigator, warrants delaying the dose of study medication.

Participants who require delay of nivolumab/ipilimumab should be re-evaluated weekly or more frequently if clinically indicated and resume nivolumab/ipilimumab dosing when re-treatment criteria are met.

Further detail on immune related adverse event management algorithm is described in [Appendix 5](#) for the following categories:

- GI Adverse Event
- Renal Adverse Event
- Pulmonary Adverse Event
- Hepatic Adverse Event
- Endocrinopathy Management
- Skin Adverse Event
- Neurological Adverse Event
- Myocarditis Adverse Event

7.4.2 Criteria to Resume Treatment with Nivolumab or Ipilimumab

Participants may resume treatment with study drug when the drug-related AE(s) resolve to Grade ≤ 1 or baseline value, with the following exceptions:

- Participants may resume treatment in the presence of Grade 2 fatigue;
- Participants who have not experienced a Grade 3 drug-related skin AE may resume treatment in the presence of Grade 2 skin toxicity;
- For participants with Grade 2 AST, ALT and/or Total Bilirubin Abnormalities, dosing may resume when laboratory values return to baseline and management with corticosteroids, if needed, is complete;
- Drug-related pulmonary toxicity, diarrhea or colitis must have resolved to baseline before treatment is resumed. Participants with persistent Grade 1 pneumonitis after completion of a steroid taper over at least 1 month may be eligible for retreatment if discussed with and approved by BMS Medical Monitor/designee;
- Participants with drug-related endocrinopathies adequately controlled with only physiologic hormone replacement may resume treatment after consultation with the BMS Medical Monitor/designee. Adrenal insufficiency requires discontinuation regardless of control with hormone replacement.

7.4.3 Treatment of Nivolumab- or Ipilimumab-related Infusion Reactions

Since nivolumab and ipilimumab contains only human immunoglobulin protein sequences, it is unlikely to be immunogenic and induce infusion or hypersensitivity reactions. However, if such a reaction were to occur, it might manifest with fever, chills, rigors, headache, rash, pruritus, arthralgias, hypotension, hypertension, bronchospasm, or other allergic-like reactions. All Grade 3 or 4 infusion reactions should be reported within 24 hours to the study medical monitor/designee and reported as an SAE if it meets the criteria. Infusion reactions should be graded according to NCI CTCAE (version 4.0) guidelines.

Treatment recommendations are provided below and may be modified based on local treatment standards and guidelines, as appropriate:

For Grade 1 symptoms (mild reaction; infusion interruption not indicated; intervention not indicated):

- Remain at bedside and monitor participant until recovery from symptoms. The following prophylactic premedications are recommended for future infusions: diphenhydramine 50 mg (or equivalent) and/or acetaminophen/paracetamol 325 to 1000 mg at least 30 minutes before additional nivolumab administrations.

For Grade 2 symptoms: (moderate reaction required therapy or infusion interruption but responds promptly to symptomatic treatment (eg, antihistamines, non-steroidal anti-inflammatory drugs, narcotics, corticosteroids, bronchodilators, IV fluids); prophylactic medications indicated for ≤ 24 hours):

- Stop the study drug infusion, begin an IV infusion of normal saline, and treat the participant with diphenhydramine 50 mg IV (or equivalent) and/or acetaminophen/paracetamol 325 to 1000 mg; remain at bedside and monitor participant until resolution of symptoms. Corticosteroid and/or bronchodilator therapy may also be administered as appropriate. If the infusion is interrupted, then restart the infusion at 50% of the original infusion rate when symptoms resolve; if no further complications ensue after 30 minutes, the rate may be increased to 100% of the original infusion rate. Monitor participant closely. If symptoms recur, then no further study medication will be administered at that visit.
- For future infusions, the following prophylactic premedications are recommended: diphenhydramine 50 mg (or equivalent) and/or acetaminophen/paracetamol 325 to 1000 mg should be administered at least 30 minutes before nivolumab and/or ipilimumab infusions. If necessary, corticosteroids (up to 25 mg of hydrocortisone or equivalent) may be used.

For Grade 3 or 4 symptoms: (severe reaction, Grade 3: prolonged [ie, not rapidly responsive to symptomatic medication and/or brief interruption of infusion]; recurrence of symptoms following initial improvement; hospitalization indicated for other clinical sequelae (eg, renal impairment, pulmonary infiltrates). Grade 4: Life threatening; pressor or ventilatory support indicated):

- Immediately discontinue infusion of study drug. Begin an IV infusion of normal saline and treat the participant as follows: Recommend bronchodilators, epinephrine 0.2 to 1 mg of a

1:1000 solution for subcutaneous administration or 0.1 to 0.25 mg of a 1:10,000 solution injected slowly for IV administration, and/or diphenhydramine 50 mg IV with methylprednisolone 100 mg IV (or equivalent), as needed. Participant should be monitored until the Investigator is comfortable that the symptoms will not recur. Study drug will be permanently discontinued. Investigators should follow their institutional guidelines for the treatment of anaphylaxis. Remain at bedside and monitor participant until recovery of the symptoms.

In case of late-occurring hypersensitivity symptoms (eg, appearance of a localized or generalized pruritus within 1 week after treatment), symptomatic treatment may be given (eg, oral antihistamine or corticosteroids).

7.4.4 Trametinib Dose Delay/Modifications

7.4.4.1 General Guidelines for Trametinib Related Toxicities

General guidelines regarding management and dose reduction for adverse events that are considered by the investigator to be related to trametinib are provided in Table 7.4.4.1-1. The severity of adverse events will be graded utilizing the CTCAE v 4.0. Guidelines for specific trametinib related toxicities as listed in [Section 7.4.4.2](#) are provided in [Appendix 6](#).

Table 7.4.4.1-1: Dose Delay and Modification for Events Considered Related to Trametinib (excluding pyrexia)

CTCAE Grade	Action and Dose Modification
Grade 1	
Continue trametinib at current dose levelMonitor closelyProvide supportive care according to institutional standards
Grade 2	
Interrupt trametinib if clinically indicatedMonitor closelyProvide supportive care according to institutional standardsWhen toxicity resolves to Grade 1 or baseline, restart trametinib at current dose level
Grade 3	
Interrupt trametinib if clinically indicatedMonitor closelyProvide supportive care according to institutional standardsWhen toxicity resolves to Grade 1 or baseline, restart trametinib reduced by one dose levelIf the Grade 3 toxicity recurs, interrupt trametinibWhen toxicity resolves to Grade 1 or baseline, restart trametinib reduced by another dose level
Grade 4	
Interrupt trametinibMonitor closelyProvide supportive care according to institutional standardsIf event resolves to Grade 1 or baseline discuss potential continuation of trametinib with the Medical Monitor/designee; if continuation of treatment agreed then restart trametinib at dose reduced by one dose level

Table 7.4.4.1-1: Dose Delay and Modification for Events Considered Related to Trametinib (excluding pyrexia)

CTCAE Grade	Action and Dose Modification
	
 • If event does not resolve permanently discontinue trametinib 
Note: Approval from the Medical Monitor/designee is required to restart study treatment after ≥ 21 days of interruption.
 
Note: In participants who experience retinal vein occlusion, trametinib treatment should be permanently discontinued.

7.4.4.2 Guidelines for Specific Trametinib-related Toxicities

Trametinib dose modification guidelines for specific clinically significant toxicities and common toxicities that may be related to trametinib are outlined in [Appendix 6](#):

- Rash
- Diarrhea
- Ejection fraction changes
- Hypertension
- Pneumonitis
- Visual changes
- Liver chemistry elevation.
- Hand and foot syndrome
- Pyrexia

Refer to the relevant sections of Appendix 6 for dose modification guidelines for these specific adverse events as listed above.

7.4.4.3 Dose Modification for Trametinib

[Table 7.4.4.3-1](#) describes the dose /schedule to be used for any necessary dose modifications for trametinib.

- For Grade 2 or 3 laboratory abnormalities that are considered unrelated to the study treatment or those that are reversible in <48 hrs (except for liver enzymes) such as electrolyte abnormalities may continue without dose reductions. Modification of trametinib dosing frequency is not permitted, except dose delay to manage toxicity per dose modification guideline (Appendix 6).
- A maximum of 2 trametinib dose level reductions are allowed for Part 1 and Part 1A. For Parts 1B and 2, a maximum of 1 trametinib dose level reduction is allowed. If a third dose level/frequency reduction is required for Part 1 or Part 1A, second for Parts 1B and 2, treatment will be permanently discontinued.

- If a dose reduction of trametinib is required (Parts 1B and 2), but the toxicity resolves and no additional toxicities are seen after 4 weeks of treatment, the dose of trametinib may be re-escalated but should not exceed 1.5 mg once a day or the dose determined from dose optimization evaluation, whichever is lower. Dose re-escalation may NOT be permitted for specific toxicities as described in [Appendix 6](#).
- The minimum daily dose of trametinib that is permissible on study is 1.0 mg. If participants require a dose reduction below 1.0 mg, they should be permanently discontinued from trametinib.

Table 7.4.4.3-1: Potential Trametinib Dose Levels in Part 1B and Part 2

Daily Dose Level	Dose/Day
Maximum	1.5 mg once a day
Minimum	1.0 mg once a day

7.4.5 Criteria to Resume Treatment with Trametinib

Treatment with trametinib may be delayed for up to 21 days to allow resolution of toxicity, or based on investigator discretion (eg, scheduling issues). If the investigator and the Medical Monitor/designee conclude that continued treatment will benefit a participant who has experienced a treatment delay > 21 days, then the participant may continue treatment with the approval of the Medical Monitor/designee. If a dose delay continues for 10 weeks or more, then trametinib should be permanently discontinued for toxicities considered related to study drug.

7.4.6 Dose Modification for Regorafenib

If dose modifications are required, reduce the dose in 40 mg (1 tablet) increments; the lowest recommended daily dose of regorafenib is 80 mg daily. The following dose modification is provided as a recommendation. Local product labels and/or institutional guidelines should be followed if they are more conservative than the recommendations below.

Interrupt regorafenib for the following:

- Grade 2 hand-foot skin reaction (HFSR) [palmar-plantar erythrodysesthesia (PPES)] that is recurrent or does not improve within 7 days despite dose reduction; interrupt therapy for a minimum of 7 days for Grade 3 HFSR (refer to [Table 7.4.6-2](#) for additional requirements)
- Symptomatic Grade 2 hypertension
- Any Grade 3 or 4 adverse reaction
- Worsening infection of any grade
- Reduce the dose of regorafenib to 120 mg:
 - For the first occurrence of Grade 2 HFSR of any duration (refer to [Table 7.4.6-2](#) for additional requirements)
 - After recovery of any Grade 3 or 4 adverse reactions except infection

- For Grade 3 AST/ALT elevation, only resume if the potential benefit outweighs the risk of hepatotoxicity (refer to Table 7.4.6-1 for additional requirements)

Reduce the dose of regorafenib to 80 mg:

- For re-occurrence of Grade 2 HFSR at the 120 mg dose (refer to [Table 7.4.6-2](#) for additional requirements). After recovery of any Grade 3 or 4 adverse reaction at the 120 mg dose (except hepatotoxicity or infection)

Table 7.4.6-1: Recommended Measures and Dose Modifications in Case of Drug-related Liver Function Test Abnormalities

Observed Elevations of ALT and/or AST	Occurrence	Recommended Measures and Dose Modification
≤ 5 times ULN (maximum Grade 2)	Any occurrence	Continue regorafenib treatment. Monitor liver function weekly until transaminases return to < 3 times ULN (Grade 1) or baseline.
> 5 times ULN ≤ 20 times ULN (Grade 3)	1st occurrence	Interrupt regorafenib treatment. Monitor transaminases weekly until they return to < 3 times ULN or baseline. Restart: If the potential benefit outweighs the risk of hepatotoxicity, re-start regorafenib treatment, reduce dose by 40 mg (1 tablet), and monitor liver function weekly for at least 4 weeks.
	Re-occurrence	Discontinue treatment with regorafenib permanently.
> 20 times ULN (Grade 4)	Any occurrence	Discontinue treatment with regorafenib permanently.
> 3 times ULN (Grade 2 or higher) with concurrent bilirubin > 2 times ULN	Any occurrence	Discontinue treatment with regorafenib permanently. Monitor liver function weekly until resolution or return to baseline. Exception: Patients with Gilbert's syndrome who develop elevated transaminases should be managed as per the above outlined recommendations for the respective observed elevation of ALT and/or AST.

Source: Modified from Table 2 of regorafenib SmPC

Table 7.4.6-2: Recommended Dose Modifications and Measures for HFSR

Skin Toxicity Grade	Occurrence	Recommended Dose Modification and Measures
Grade 1	Any	Maintain dose level and immediately institute supportive measures for symptomatic relief.
Grade 2	1st occurrence	Decrease dose by 40 mg (1 tablet) and immediately institute supportive measures. If no improvement occurs despite dose reduction, interrupt therapy for a minimum of 7 days, until toxicity resolves to Grade 0-1. A dose re-escalation is permitted at the discretion of the physician.
	No improvement within 7 days or 2nd occurrence	Interrupt therapy until toxicity resolves to Grade 0-1. When re-starting treatment, decrease dose by 40 mg (1 tablet). A dose re-escalation is permitted at the discretion of the physician.
	3rd occurrence	Interrupt therapy until toxicity resolves to Grade 0-1. When re-starting treatment, decrease dose by 40 mg (1 tablet). A dose re-escalation is permitted at the discretion of the physician.
	4th occurrence	Discontinue treatment with regorafenib permanently.
Grade 3	1st occurrence	Institute supportive measures immediately. Interrupt therapy for a minimum of 7 days until toxicity resolves to Grade 0-1. When re-starting treatment, decrease dose by 40 mg (1 tablet). A dose re-escalation is permitted at the discretion of the physician.
	2nd occurrence	Institute supportive measures immediately. Interrupt therapy for a minimum of 7 days until toxicity resolves to Grade 0-1. When re-starting treatment, decrease dose by 40 mg (1 tablet).
	3rd occurrence	Discontinue treatment with regorafenib permanently.

Source: Modified from Table 1 of regorafenib SmPC

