7.1.4.3 Regorafenib Dosing

Please refer to local product label and institutional guidelines for further details.

The recommended dose of regorafenib is 160 mg (four 40 mg tablets) taken orally once daily for the first 21 days of each 28-day cycle. Continue treatment until disease progression, unacceptable toxicity, withdrawal of consent, or the study ends, whichever occurs first.

The participant should take regorafenib at the same time each day. Swallow tablet as a whole with water after a low-fat meal that contains less than 600 calories and less than 30% fat. The participant should not take 2 doses of regorafenib on the same day to make up for a missed dose from the previous day. Any missed doses reported by the participant should be recorded in the participant's source documents and in the participant's diary.

Initiation of the Next Treatment Cycle:

- The next cycle will be initiated every 4 weeks with regorafenib dosing as specified in Table 7.1.4.2-1.

- If regorafenib dosing is delayed, the next cycle will start if at least 4 weeks have passed from the first dose in the current cycle to dosing re-initiation.
- The next treatment cycle may be initiated within a \pm 3-day window of scheduled dose due to scheduling conflict.

7.1.5 Part 1A Completed (Triplet Regimen, Cohort 2 Group and Cohort 3 Group: Closed for Enrollment)

The dose optimization phase of the study (Parts 1 and 1A) are completed. Enrollment is closed in Part 1 and Part 1A cohorts.

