8.1.4 Regorafenib Dose Discontinuation

Discontinue regorafenib permanently for any of the following (local product label and institutional guidelines should be followed if they are more conservative):

- Failure to tolerate 80 mg dose
- Any occurrence of AST or ALT > 20× ULN
- Any occurrence of AST or ALT > 3× ULN with concurrent bilirubin > 2× ULN, except in participants with Gilbert's syndrome
- Re-occurrence of AST or ALT > 5× ULN despite dose reduction to 120 mg
- Gastrointestinal perforation or fistula
- Severe or life-threatening hemorrhage
- Reversible posterior leukoencephalopathy syndrome
- Wound dehiscence
- For any Grade 4 adverse reaction; only resume if the potential benefit outweighs the risks
- Any event that leads to delay in dosing for > 10 weeks from the previous dose requires discontinuation with the following exception:
 - Dosing delays > 10 weeks that occur for non-drug-related reasons may be allowed if approved by the BMS Medical Monitor. Prior to re-initiating treatment in a subject with a dosing delay lasting > 10 weeks, the BMS Medical Monitor must be consulted. Tumor assessments should continue as per protocol even if dosing is delayed.
- Any AE, laboratory abnormality, or intercurrent illness which, in the judgment of the investigator, presents a substantial clinical risk to the subject with continued treatment

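### Without re-escalation, the Grade 2 hand-foot skin reaction rows of Table 7.4.6-2 lead to regorafenib 40 mg, below the 80 mg lowest dose stated in Section 7.4.6

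*Combined protocol and SAP*

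**What the plan says.** Section 7.1.4.3 gives the starting point for Cohort 5: "The recommended dose of regorafenib is 160 mg (four 40 mg tablets) taken orally once daily for the first 21 days of each 28-day cycle".

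The text of Section 7.4.6 tells sites to "reduce the dose in 40 mg (1 tablet) increments" and adds that "the lowest recommended daily dose of regorafenib is 80 mg daily". It names two reduced doses. The dose goes to 120 mg "For the first occurrence of Grade 2 HFSR of any duration", and to 80 mg "For re-occurrence of Grade 2 HFSR at the 120 mg dose". It names no step below 80 mg. For HFSR it sends the reader to Table 7.4.6-2 for additional requirements.

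For Grade 2 HFSR, Table 7.4.6-2 has four rows:

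- First occurrence: "Decrease dose by 40 mg (1 tablet) and immediately institute supportive measures".
- No improvement within 7 days, or second occurrence: "Interrupt therapy until toxicity resolves to Grade 0-1. When re-starting treatment, decrease dose by 40 mg (1 tablet".
- Third occurrence: the same instruction as the row before.
- Fourth occurrence: permanent discontinuation.

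The first three rows allow re-escalation at the physician's discretion. For Grade 3 HFSR there are two 40 mg reductions and a permanent stop at the third occurrence.

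Section 8.1.4 lists "Failure to tolerate 80 mg dose" among the reasons for stopping regorafenib permanently. Section 8.1 makes discontinuation compulsory for the criteria in Sections 8.1.1 to 8.1.4. The modification rules in Section 7.4.6 are described as recommendations, and a local label or institutional guideline applies where it is more conservative.

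**The concern.** The table expresses each reduction as a relative step, while the text of the same section sets an absolute lowest dose. The Grade 2 sequence has one more step than there is room for between 160 mg and 80 mg. Nothing in the table caps the third step or makes it depend on an earlier re-escalation.

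What is at stake is the instruction for a control-arm participant who is already at 80 mg and has another Grade 2 reaction. The third-occurrence row says to resume one tablet lower. The text of Section 7.4.6 says there is no lower recommended dose. Section 8.1.4 may require a permanent stop. Two sites reading in good faith could act differently.

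**Working it through.** **Inputs**

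- Starting dose: 160 mg (Section 7.1.4.3)
- Step: 40 mg (Section 7.4.6 text and Table 7.4.6-2)
- Stated lowest dose: 80 mg (Section 7.4.6 text)
- Reductions before the permanent stop: three for Grade 2, two for Grade 3 (Table 7.4.6-2)

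Dose after n reductions without re-escalation = 160 - 40n mg.

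**Reproducing the 80 mg figure.** The text names two reductions, so 160 - 2 x 40 = 80 mg. The Grade 3 rows give the same: 160, 120, 80, then stop. Both agree with the stated lowest dose.

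**Grade 2 rows, no re-escalation**

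| Occurrence | Dose before | Dose directed |
|---|---|---|
| 1st | 160 mg | 120 mg |
| 2nd (or no improvement within 7 days) | 120 mg | 80 mg |
| 3rd | 80 mg | 40 mg |
| 4th | 40 mg | permanent stop |

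160 - 3 x 40 = 40 mg, which is 40 mg below the stated lowest dose.

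**Grade 2 rows with re-escalation.** Allow the dose to rise by whole steps, to at most 160 mg, between one occurrence and the next. There are then five possible paths to the third reduction:

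1. 160 to 120, 120 to 80, 80 to 40: below 80 mg.
2. 160 to 120, 120 to 80, back to 120, then 80.
3. 160 to 120, 120 to 80, back to 160, then 120.
4. 160 to 120, back to 160, then 120, then 80.
5. 160 to 120, back to 160, then 120, back to 160, then 120.

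Paths 2 to 5 stay at or above 80 mg. Path 1, where the optional step is not taken, does not. These are counts of possible paths, not probabilities.

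**Mixed grades.** The table does not say whether occurrences of different grades are counted together. If each grade is counted separately, two examples without re-escalation are:

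- Grade 3 first occurrence (160 to 120), Grade 2 first (120 to 80), Grade 2 second (80 to 40).
- Grade 2 first (160 to 120), Grade 3 first (120 to 80), Grade 3 second (80 to 40).

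Both pass below 80 mg, so the gap is not confined to three Grade 2 events.

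**Section 8.1.4.** Suppose a third Grade 2 reaction occurs at 80 mg. If it counts as failure to tolerate 80 mg, Section 8.1.4 requires a permanent stop, while the table directs a restart at a lower dose. If it does not count, Section 8.1.4 is silent, and the conflict is only between the table and the lowest dose in Section 7.4.6. The protocol does not define the phrase.

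**The case against.** The strongest reply is that the section already limits its own table. The opening sentence of Section 7.4.6 gives the step and the lowest dose together, the table sits beneath it, and its rows state a decrement and not a target. No passage names 40 mg as a daily dose. The third-occurrence row also has a coherent use, because a participant who was re-escalated may be at 120 or 160 mg when it applies. Finally, the documents rank the instructions: Section 7.4.6 is a recommendation, whereas Section 8.1 is compulsory.

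Much of this is fair. A careful reader could combine the passages in that way, but none of them says to. The text refers sites to the table for additional requirements, and the table neither repeats the lowest dose nor ties the third step to re-escalation. By contrast, Section 7.4.4.3 states the minimum trametinib dose together with what follows if a participant would need less. Local labels may also settle the question, but they are not part of the documents, and they prevail only where they are more conservative.

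Two stronger readings are tempting. A reader might infer that the table and Section 8.1.4 always give opposite orders at 80 mg. That does not follow, because it depends on the undefined failure to tolerate, and a recommendation is not on the same footing as a compulsory stop. A reader might also infer that comparator exposure or time on treatment in Part 2 is materially affected. The documents do not support that at this scale. Cohort 5 has about 40 participants (Section 5.1.3), and Table 3.2.2-1 gives a median PFS of 1.9 months on regorafenib, roughly two 28-day cycles, so few are likely to have three reactions without re-escalation.

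**Conclusion.** The inconsistency is real and narrow. Followed row by row from 160 mg without re-escalation, the Grade 2 part of Table 7.4.6-2 directs 40 mg, against a stated lowest recommended dose of 80 mg. The Grade 3 rows alone respect the lowest dose. Mixed sequences need not, if each grade is counted separately. A further conflict with Sections 8.1 and 8.1.4 exists only if a Grade 2 reaction at 80 mg is taken as failure to tolerate that dose.

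The conclusion assumes a 160 mg start and no use of the discretionary re-escalation. The number of participants affected cannot be computed from the documents and is probably small. There is no effect on sample size, alpha or power. This is an inconsistent dosing instruction in the control arm, minor for the analysis but worth correcting. Enrollment closed on 30-Nov-2022, so any benefit is for participants still on regorafenib; Cohort 5 has no maximum treatment duration, and Table 2-9 provides for continued dosing if closure is delayed.

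**What to change.** Reconcile three places so that a participant already at 80 mg has one instruction: the HFSR rows of Table 7.4.6-2, in particular the Grade 2 third-occurrence row; the lowest daily dose stated in the text of Section 7.4.6; and the failure-to-tolerate criterion in Section 8.1.4. The reconciled text should make clear whether a further Grade 2 reaction at 80 mg falls under that criterion, and how occurrences are counted when grades are mixed. Which dose or stopping rule is right is for the sponsor's clinical team; this review takes no view.

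The cost is a short table note or cross-reference. It needs no new data and no change to the analysis.
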